#### DESCRIPTION OF ASSESSMENTS:

A rater blind to the treatment arm will administer the following tests:

*Visual Analogue Scale (VAS) for Pain:* The VAS is a common assessment used which asks subjects to self-reportedly measure their pain on a visual scale (i.e., unbearable to none). We will use a VAS to determine subjects' pain scores. Subjects will rate their pain from 0 – indicating no pain at all, to 10 – indicating the worst pain felt. This scale is also colored, from green (at 0) to red (at 10), as a visual indicator of pain. This assessment tool is frequently used in many research studies evaluating pain levels [15, 27, 34, 35].

*Visual Analogue Scale (VAS) for Stump Pain:* any painful sensation in the stump. Subjects will rate their stump pain from 0 – indicating no pain at all, to 10 – indicating the worst pain felt. The scale will include colors to help in identifying the correct response [15].

*Visual Analog Scale (VAS) for Phantom Limb Sensation:* all non-painful sensations in the amputated part of the limb. Subjects will be presented with a scale starting at 0- No phantom limb sensation, to 10 – Full sensation of the amputated limb. The scale will include colors to help in identifying the correct response [15].

*Visual Analog Scale (VAS) for Phantom Limb telescoping:* refers to the shrinking and retraction of the phantom towards the residual limb. Subjects will be presented with a scale starting at 0 - indicated that the phantom was enlarged, and 10 meant that the phantom was completely retracted into the stump the scale will include colors to help in identifying the correct response [15].

*Adapted Groningen Questionnaire after Arm Amputation:* This questionnaire is originally meant to obtain information's concerning complaints that may be developed after arm amputation. We adapted the current arm version for lower limb amputation. This questionnaire [36] has been used in several clinical trials assessing PLP.

*Pain and medication diary:* To help monitor pain levels and medication use information, as well as safety. Subjects will be asked to record the number of phantom limb episodes on a daily basis, using a pain diary. They will record the intensity of the strongest episode as well as phantom limb sensation and stump pain on a colored visual analog scale included in the diary, where 0 represents no pain at all and 10 represents the highest pain the patient has ever felt. Moreover subjects will record their current medications and dosages daily in a pain medication diary, until completion of the study.

*Beck Depression Inventory:* This self-report inventory consists of 21 multiple-choice questions and is widely used method to classify depression severity. It assesses for the presence of several symptoms related to depression, such as irritability, hopelessness and decreased cognitive performance. Physical symptoms such as weight loss and fatigue are also included. This instrument has been used previously to evaluate depression severity in patients with phantom limb pain [37], as well as in other chronic pain conditions [31, 38, 39]. If the subject appears at-suicidal risk (detected by the BDI questionnaire- as defined by a score of  $\geq 1$  on question 9), the medical coverage will be contacted immediately by research staff to provide further evaluation and action to protect the subject (i.e. if the subject needs to be escorted or referred to the MGH ED Acute Psychiatry Service). In addition, if a subject has moderate to severe depression (defined by a score of  $\geq 20$  in the Beck Depression Inventory), the investigator will strongly recommend the subject search for depression management centers and encourage them to speak to their primary care physician). If the BDI questionnaire is performed over the phone (visit 16) the same procedure described above will be performed over the phone by the research staff (the research staff will discuss with the medical coverage and follow his/her plan of action according to above while subject is on the phone).

*Beck Anxiety Inventory:* This self-report inventory consists of 21 multiple-choice questions about how the subject has been feeling in the last week, expressed as common symptoms of anxiety (such as numbness and tingling, sweating not due to heat, and fear of the worst happening). It is designed for an age range of 17–80 years old. Each question has the same set of four possible answer choices, which are arranged in columns and are answered by marking the appropriate one with a cross [40].

*Mini Mental State examination (MMSE):* This is a sensitive, valid and reliable 30-point questionnaire that is used extensively in clinical and research settings to measure cognitive impairment. This instrument will be used as a brief screening of cognitive abilities. It will be used as a baseline evaluation [41].

*Quality of Life Assessment (Short version of SF-36):* The short version of the SF-36 health survey is used as a measurement of quality of life. It provides a profile of functional health and well-being scores. It is also used as a psychometrical index of physical and mental health. This

instrument is widely used as a quality of life assessment in patients after an amputation and those suffering from phantom limb pain [42-45].

*Stroop test:* In this task the subject is presented with names of colors written in the same color or in a different color, thus on the one hand the word names a color (red) and is written in another color (blue). In this task, the automatized behavior (reading) is in conflict with the desired response (naming the color). The Subject has to inhibit/suppress the automatic response of reading and naming the color the word is written in. The Stroop is one of the most commonly used tools for determining attentional problems, also used to assess executive function and working memory [46, 47]. Stroop test will be applied as a preliminary safety assessment of cognitive changes from baseline to post and follow-up visits.

*Side Effects Questionnaire for tDCS:* At each stimulation session, subjects will complete a questionnaire to evaluate potential adverse effects of tDCS (tingling, burning sensation, headache, neck pain, mood alterations) and mirror therapy (anxiety, grief, dizziness) on a 4-point scale (None, mild, moderate and severe). The subjects will be asked whether they have experienced any side effects in an open-ended manner and they will then be specifically asked about headache, neck pain, scalp pain, scalp burns, tingling, skin redness, sleepiness, trouble concentrating, and acute mood change. If any side effects are reported, the degree of relatedness to the intervention will be assessed on a 5-point scale. This type of adverse events questionnaire has been used frequently in our previous tDCS studies [31], including in patients with phantom limb pain [48].

*Side Effects Questionnaire for TMS:* At each TMS assessment session, subjects will complete a questionnaire to evaluate potential adverse effects of rTMS (headache, neck pain, itching and redness at the site of stimulation) on a 5-point scale [49].

*tDCS blinding questionnaire:* after the stimulation session, subjects will complete a questionnaire to determine if our blinding methods were effective. We are using a 30s sham montage, just as we use in our other trials, keeping the device on the subject for the duration of the session [50].

*Patient's Global Impression of Change scale:* subjects will complete a questionnaire to assess their perception of change (if any) in the activity limitations, symptoms, emotions and overall quality of life after their participation in intervention's visits of the trial [51].

*Single and Paired Pulse TMS:* Subjects will undergo several sessions of TMS to assess cortical excitability and cortical reorganization. For TMS assessment we will use Magstim BiStim^2 TMS device (Magstim ®). We will study the most distal muscle (i.e. biceps or quadriceps) of the amputated limb. In addition, if MEP is not obtained in the leg, the MEP will be assessed in the first dorsal interosseous. We will initially investigate changes in cortical excitability evaluating the motor evoked potential (MEP) and the resting motor threshold (MT); we will use the same methods as in our previous study [52], as well as short-interval intracortical inhibition (SICI) and intracortical facilitation (ICF) using the paired-pulse technique. We will investigate both contralateral and ipsilateral primary motor cortex (in relation to the amputated limb). We will investigate the resting motor threshold (MT), measured following the technique as described by

Rossini et al., where resting MT will be defined as the lowest stimulus intensity to evoke a MEP of 50  $\mu$ V in five of 10 trials in the relaxed muscle [53]. We will record this in both primary motor cortices when possible. For the MEP study, we will initially adjust TMS intensity to achieve a baseline MEP in the selected muscle of about 1 mV peak-to-peak amplitude before intervention. Stimulation intensity will be kept constant for each subject throughout the evaluation sessions. The MEPs will be recorded and stored in a computer for off-line analysis. We will record 10 MEPs for each time point (immediately before and after the tDCS treatment for both motor cortices) and average their peak-to-peak amplitude and area-under-the-curve. The short-interval intracortical inhibition (SICI) and intracortical facilitation (ICF) will be measured using the paired-pulse technique [54], in both primary motor cortices. A suprathreshold test stimulus adjusted to an MEP amplitude of 1 mV will be preceded by a subthreshold conditioning stimulus (CS; 80% MT) at interstimulus intervals of 2, 3, 6, 9, 10, and 12 ms, which samples inhibitory (2, 3ms, SICI) and excitatory (9, 10, 12 ms, ICF) windows, respectively. Ten stimuli will be applied at each interval in a randomized order. The percentage of inhibition or facilitation for each ISI before and after treatment will be calculated. Cortical mapping: eight stimulations at 120 % stimulus of rMT intensity (posterior to anterior current) will be delivered to each of fifteen sites forming a 3 x 5 grid, with a constant 1.5 cm distance between sites, over the primary motor cortex (M1). At each stimulation site, the peak-to-peak amplitudes of the recorded motor evoked potentials (MEPs) will be measured and averaged offline.

The map CoG will be computed for the medio-lateral (x) coordinates using the formula:  $CoG_x = (\sum x_i * MEP_i) / \sum MEP_i$  where  $MEP_i$  represents the mean amplitude of the MEPs produced at one site. The MV will be calculated as the sum of the average MEP amplitude at each active site, where an active site was defined as a site at which the mean MEP amplitude was at least 0.05mV.

*Functional magnetic resonance imaging (fMRI):* to quantify maladaptive cortical reorganization before and after treatment. Each fMRI exam will be performed at the Boston University Medical Center, Center of Biomedical Imaging; this is a fee-for-service, and they are not engaged in the research. The BU Medical Center has an extensive and expanding inventory of state-of-the-art imaging facilities. One of the core technologies being developed and used at the center are Magnetic Resonance Imaging (MRI) and Spectroscopy (MRS). Additionally for this visit an fMRI survey (BU Safety Screening Form )form will be filled out by the radiation technician or study investigator (NINDS CDE) [26].

We decided to conduct a longitudinal design sessions (baseline and post-treatment). To minimize the limitations of this longitudinal analysis we will use an algorithm of initialization in the FreeSurfer processing stream [55].

The fMRI sessions will be conducted using the following stimuli and task detailed below and in Figure 2.

[figure not shown]

Figure 2. The scheme shows tasks performed during fMRI sessions.

We based this design in an experiment investigating activation of motor networks associated with observation and imagination of the lower limbs movements [56]. The stimuli will consist of the movement of the lower limb (non amputated limb), followed by the same movement but now the participant will be able to observe his/her leg moving and the leg image in the mirror through a online video.

The following three conditions will be therefore investigated:

1. Movement of the leg (MOV-LEG): the subjects will perform movements of the non amputated leg. Each participant will be instructed about the type and pace of the movements.
2. Movement of the leg observing the mirror (MIR-LEG): the subjects will perform the same movements from the previous condition, looking the mirror image of the intact leg in an online video. Each participant will be instructed about the type, pace and video.
3. Rest condition: the subjects will rest during this period and will be instructed to not perform any kind of movements during this period.

Each of these conditions will have the same length – 20 seconds. The fMRI session will have four runs that will contain 6 blocks (6 of each condition). The order of the conditions will be randomized. For the analysis we will determine the ROI of interest (primary sensory motor cortex of the lower limbs) and first determine the ratio of activation between the MOV-LEG and MIR-LEG (in the respective ROI of interest – contralateral to the respective leg). Using this coefficient we will then compare across the different conditions. Our hypothesis is that the combined group (tDCS and mirror therapy) will have a greater activation than any therapy alone

and also the no therapy group (sham tDCS and covered mirror). This effect will also be correlated with pain reduction.

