**Visit 3**

fMRI Evaluation – (Approximate Time: 1 hour)

*\*\*Visits 1-3 may be completed on the same day or broken up into two or three separate visits as the subject prefers*

**Visit 4 – 12** (Approx Time: 45 minutes)

Intervention visits: tDCS + Mirror Therapy

*This visit will be scheduled within 1 week after the baseline measurements are done.*

In the first 2 weeks subjects will receive tDCS (\*sham or active) and mirror therapy (sham or active). There will be 10 stimulation visits to be completed in these 2 weeks (ideally Monday to Friday, 5 days each week). The subject will receive 20 minutes either of active or sham tDCS per day and 15 min of active or sham mirror therapy sessions. The subjects will receive the intervention according to the prior randomized group.

Before stimulation, the subject will complete the following assessments:

- VAS Phantom Limb Pain
- VAS for Stump pain
- VAS for Phantom Limb Sensation
- VAS for Phantom Limb Telescoping

After each session, subjects will complete the following assessments:

- Side Effects Questionnaire for tDCS
- VAS Phantom Limb Pain
- VAS for Stump pain
- VAS for Phantom Limb Sensation
- VAS for Phantom Limb Telescoping

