**Visit 13**

Last day of tDCS session + Mirror Therapy – (Approx Time: 2 hours)

Before stimulation, the subject will complete the following assessments:

- VAS Phantom Limb Pain
- VAS for Stump pain
- VAS for Phantom Limb Sensation
- VAS for Phantom Limb Telescoping

After each session, subjects will complete the following assessments:

- Visual Analogue Scale (VAS) for phantom limb pain
- Visual Analogue Scale (VAS) for Stump pain
- Visual Analog Scale (VAS) for Phantom Limb Sensation
- Visual Analog Scale (VAS) for Phantom Limb Telescoping
- Pain and medication use diary
- Stroop Test
- Beck Anxiety Inventory

- Beck Depression Inventory
- Side Effects Questionnaire for tDCS
- Blinding Questionnaire
- Single and paired pulse TMS
- Side Effects Questionnaire for TMS

**After the first 2 Weeks combined intervention (sham/active tDCS plus sham/real mirror therapy) at the Neuromodulation Center in front of the therapist, subjects will continue mirror therapy for 10 additional sessions over the course of ~ 2 weeks at home.**

2 weeks of home Mirror Therapy – (Approx Time: 15 min)

During this 2 week period the co-investigator will try to contact the subjects 3 times per week to assess adherence to the MT treatment and acquire pain diary and medication changes data. We are going to try maximum 2 attempts per day.

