**Visit 17:**

Last Follow Up Visit - (Approx Time: 2 hours)

*This visit will be schedule ~eight weeks (+/- 5 days) after the last MT home session and the following assessments will be performed:*

[figure not shown]
- Visual Analogue Scale (VAS) for phantom limb pain
- Visual Analogue Scale (VAS) for Stump pain
- Visual Analog Scale (VAS) for Phantom Limb Sensation
- Visual Analog Scale (VAS) for Phantom Limb Telescoping
- Pain Medication uses diary.
- Stroop Test.
- Health Survey SF-36.
- Beck Anxiety Inventory
- Beck Depression Inventory
- Single and paired pulse TMS
- Side Effects Questionnaire for TMS
- Blinding questionnaire

[figure not shown]
*\*\*After visit 14 until the end of the trial participation, the co-investigator will try to contact the subjects 3 times per week to acquire pain diary and medication changes data. We are going to try maximum 2 attempts per day.*

The schedule for the subjects can be seen in table 1, which illustrates the procedures that will be performed at each visit:

**Table 1:** Visits Schedule

	Consent and Screening	Baseline	fMRI Visit	Interventions Session	fMRI Visit	Follow-Up
--	------------------------------	-----------------	-------------------	------------------------------	-------------------	------------------

observed in the mirror to their phantom limb and to keep their attention focused on the task. Instructions will be explained verbally, demonstrated by a therapist, and performed by the subject in front of the therapist during the first two weeks (the MT sessions will be scheduled back-to-back with the tDCS sessions). After this training, subjects will continue MT everyday for 2 more weeks at home. Subjects will be instructed to stop MT if it intensifies their pain, and to document if this happens

- Sham Mirror Therapy (Covered MT): Subjects will be asked to perform movements in the same way that the active group but with a covered mirror.

[figure not shown]

Figure 1: Schematic view of the experiment in time points: baseline, procedures, subjects enrolled intervention, first follow-up and second follow up.

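### No structured enquiry about mirror-therapy side effects is listed for the home phase, which holds about half of the scheduled mirror sessions, and the questionnaire's two item lists disagree

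*Combined protocol and SAP*

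**What the plan says.** Under Description of Assessments, the Side Effects Questionnaire for tDCS is scheduled by stimulation: "At each stimulation session, subjects will complete a questionnaire to evaluate potential adverse effects of tDCS". The same sentence extends it to the second intervention: "and mirror therapy (anxiety, grief, dizziness) on a 4-point scale (None, mild, moderate and severe". Administration is then described. First comes an open question: "The subjects will be asked whether they have experienced any side effects in an open-ended manner". Prompts follow: "they will then be specifically asked about headache, neck pain, scalp pain, scalp burns, tingling, skin redness, sleepiness, trouble concentrating, and acute mood change". Any reported effect is rated once for its relation to the intervention.

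The visit lists agree with that timing. The form appears under Visits 4–12 and Visit 13 and at no later visit. On the number of clinic sessions the protocol says "There will be 10 stimulation visits to be completed in these 2 weeks".

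Mirror therapy goes on after stimulation ends. Under Visit 13: "subjects will continue mirror therapy for 10 additional sessions over the course of ~ 2 weeks at home". The mirror-therapy description after Table 1 instead describes daily home practice for two more weeks. The plan for calls by study staff in this phase reads: "will try to contact the subjects 3 times per week to assess adherence to the MT treatment and acquire pain diary and medication changes data". The mirror-therapy description adds: "Subjects will be instructed to stop MT if it intensifies their pain, and to document if this happens". Visit 14, which closes the mirror course, lists the side-effects form for TMS but not the one covering mirror therapy.

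**The concern.** The form is meant to cover two interventions, but its schedule follows only one of them. When tDCS ends, so does the form, although the mirror course is then only about half done. The sessions left uncovered are those in which the therapist is no longer in the room.

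Two things are at stake. First, solicited information on how mirror therapy is tolerated would come almost entirely from supervised sessions, in a factorial trial that evaluates mirror therapy alongside tDCS. Second, the protocol itself foresees that some subjects will stop because pain increases, yet the calls list adherence and no question on the reason for a stopped or skipped session. Unless the subject's own note is retrieved, such a stop may be hard to tell from ordinary non-adherence.

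A smaller issue concerns the clinic phase. If staff work from the list of prompted items, the three mirror effects may be left to the open question while the tDCS effects are prompted. Two sites that are meant to follow the same procedures could read the description differently.

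**Working it through.** **Share of mirror sessions after the form stops**

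Inputs, all from Study Procedures:
- Clinic sessions: Visits 4–12 are 9, plus Visit 13, so 9 + 1 = 10. This reproduces the stated 10 stimulation visits.
- Home sessions: 10 (Visit 13 section), or 14 if the daily wording after Table 1 means seven days a week for two weeks. The 14 is an assumption. The two descriptions must be reconciled.
- The Visit 14 section allows the last mirror session to be done at home or at the centre.

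Home share = home sessions / (clinic sessions + home-phase sessions):

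| Home-phase count | Last session at home | Last session at centre |
|---|---|---|
| 10 | 10/20 = 50.0% | 9/20 = 45.0% |
| 14 | 14/24 = 58.3% | 13/24 = 54.2% |

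Moving the last session to the centre does not bring it under the form, since Visit 14 does not list it. As planned, 132 subjects × 10 = 1,320 home-phase sessions, of which 66 × 10 = 660 are with an open mirror. At the 108 subjects assumed to remain after attrition, the total is 108 × 10 = 1,080.

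**What the other home-phase sources hold, as the documents describe them**

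| Source | Covers | Does not list |
|---|---|---|
| Daily diary | Phantom episodes, worst intensity, phantom sensation, stump pain, medication; safety is a stated purpose | Dizziness, grief, anxiety, reason for stopping |
| Instruction to stop and document | Pain increase with mirror therapy | The form that holds the note; any other effect |
| Calls, three attempted weekly | Adherence, diary, medication changes | Side effects, reason for stopping |
| Beck Anxiety Inventory, Visit 14 | Anxiety symptoms over the last week | First home week; relation to mirror therapy |
| Beck Depression Inventory, Visit 14 | Depression severity | Grief as an effect of therapy; relatedness |
| Global Impression of Change, Visit 14 | Perceived change in symptoms and emotions | Specific effects; relatedness |

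Pain worsening and mood are therefore partly covered. No source is described as asking about dizziness or grief, or as relating an event to mirror therapy.

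**The questionnaire's two item lists**

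The opening sentence names three mirror effects and a four-level scale. The prompted list has nine items: headache, neck pain, scalp pain, scalp burns, tingling, skin redness, sleepiness, trouble concentrating and acute mood change. Anxiety, grief and dizziness are all absent from it. Acute mood change overlaps in part with anxiety and grief; dizziness has no counterpart.

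**The case against.** The strongest reply is that the home weeks are not without safety data. Subjects are told to document pain that rises with mirror therapy, the diary has a safety purpose, calls are attempted three times a week, Visit 14 repeats both Beck inventories, and a physician and therapist oversee safety at each site. This stands. A reader might infer that nothing about side effects is collected at home, or that home events are captured at a rate of zero. The documents do not support that. What is missing is a structured, solicited enquiry.

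A reader might also turn the session shares into a proportion of events captured. That needs a constant event rate per session, and the documents give no rate.

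Nor do the documents support the reading that the mirror effects are never asked about in clinic. A scale with a level for no effect suggests that each named effect is rated, and the prompted list may not be exhaustive. The two sentences conflict, and that is as far as the text goes.

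Similarly, it would be too strong to say that pain-driven stopping will be recorded as non-adherence, because subjects are told to document it. What stands is that no form or call item is listed to bring that note into the data.

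Two further points hold. Collection is the same in open- and covered-mirror arms, so nothing here shows a bias in the randomised mirror contrast; and the supplied statistical section describes no tolerability analysis, so the effect on reporting is an inference. Also, Table 1 is broken, the mirror-therapy description begins mid-sentence, and the reference list continues past the last citation in the statistical section with sources on stimulation safety and MRI risk. A risk or adverse-event section may exist outside the supplied text.

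**Conclusion.** The point holds as a gap in solicited data collection. The only questionnaire covering the named mirror-therapy effects ends with stimulation, leaving 50% of scheduled mirror sessions without a structured side-effects enquiry on the explicit 10-session count. On the same count, 45% take place at home if the last session is done at the centre; the share is 58% if daily practice means 14 home sessions. Pain worsening and mood are partly covered by other means. Dizziness, grief, relatedness to mirror therapy and the retrieved reason for stopping are not. Separately, the questionnaire's description contradicts itself on whether the three effects are individually asked about.

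This is an inexpensive improvement to safety data and does not touch the primary analysis. It rests on the visit lists and assessment descriptions as supplied. Confidence is moderate because an adverse-event section elsewhere, or the intact Table 1, could supply part of what is missing. Even then, the visit lists and the questionnaire description would need to be brought into line with it.

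**What to change.** Make three changes to data collection:

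1. Administer the existing side-effects questionnaire at Visit 14, with recall covering the whole home phase.
2. Add its three mirror-therapy items (anxiety, grief, dizziness) to the three weekly home-phase calls, with one question on whether any session was stopped or skipped and why, giving more pain or another side effect as response options.
3. Reconcile the two item lists in the questionnaire's description so that the three mirror effects are prompted, and rename the form to show that it covers both interventions.

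If an adverse-event section already provides for this, a cross-reference from the visit lists and the call description is enough. Rating relatedness separately for tDCS and for mirror therapy would help attribution in a factorial trial, but is optional.

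The cost is a revised form and call script and a few minutes per call, with no new visit. Reported mirror-therapy event counts will probably be somewhat higher because more is asked, and the trial report should say so.

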## II. SPECIFIC AIMS

The specific aims of this experiment are as follows:

[figure not shown]
- **Aim 1: To evaluate the efficacy of tDCS and mirror therapy (MT) as rehabilitative tools for the management of chronic PLP patients.**

We will explore the aim 1 in a randomized factorial controlled trial in which patients will be assigned to one of four groups: active tDCS and active MT; sham tDCS and active MT; active tDCS and sham MT (which consists of using a covered mirror for the therapy); and both sham tDCS and sham MT (covered mirror).

The primary end point will be severity of pain measured by changes in PLP as indexed by a Visual Analog Scale (VAS). The study will require a total of 13 weeks to be completed. The first week, each patient will give daily reports of their pain using a VAS, accounting for their PLP experience in the past 24hs. This initial baseline week will be followed by 4 weeks of treatment (tDCS and/or MT) and a final 8-week follow-up period without any treatment to examine long-lasting effects of each therapy. *Our hypothesis is that the combined intervention (tDCS and MT) will result in a greater pain reduction as compared with any therapy alone and no therapy.*

- **Aim 2: To examine the mechanisms underlying PLP using two neurophysiological techniques.**

For each of the four groups described in aim 1, we will determine the neural correlates of the effect. We will use single-pulse and paired-pulse transcranial magnetic stimulation (TMS) to assess cortical mapping and cortical excitability changes associated with cortical reorganization. We will also use functional magnetic resonance imaging (fMRI) to assess brain changes, including the quantification of maladaptive cortical reorganization. Using fMRI, we will determine the changes in Blood-Oxygen-Level dependent activation between the sensory-motor cortex of the affected and unaffected side after the treatment. We will compare these neurophysiological parameters before and after treatment in each of the four groups. *Our hypothesis is that the combined group (tDCS and mirror therapy) will have a greater activation than any therapy alone and also than the no therapy group (sham tDCS and covered mirror). This effect will also be correlated with pain reduction.*

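### The only fMRI coefficient the plan commits to, a MOV-LEG to MIR-LEG ratio with no stated direction, cannot by itself establish greater activation and is not a clean form of the side contrast in Aim 2

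*Combined protocol and SAP*

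**What the plan says.** **II. Specific Aims, Aim 2.** The fMRI measure is a comparison of sides: "we will determine the changes in Blood-Oxygen-Level dependent activation between the sensory-motor cortex of the affected and unaffected side after the treatment". The comparison is then stated as: "We will compare these neurophysiological parameters before and after treatment in each of the four groups".

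**V. Study Procedures, Description of Assessments, fMRI entry.** There are two movement tasks and a rest condition. In MOV-LEG, "the subjects will perform movements of the non amputated leg". In MIR-LEG, "the subjects will perform the same movements from the previous condition, looking the mirror image of the intact leg in an online video". Within the sensorimotor region of interest, the analysis will "first determine the ratio of activation between the MOV-LEG and MIR-LEG", taken "in the respective ROI of interest – contralateral to the respective leg". Next comes: "Using this coefficient we will then compare across the different conditions". The entry closes with the hypothesis, "Our hypothesis is that the combined group (tDCS and mirror therapy) will have a greater activation than any therapy alone", and says that this effect will be correlated with pain reduction.

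**VI. Biostatistical Analysis.** The aim 2 text gives each condition its own regressor and plans maps for contrasts of interest on both hemispheres. It names no contrast and no model comparing the arms. The sample size section justifies fMRI by an expected BOLD change of 3 to 5%, for which 7 to 8 subjects are said to suffice.

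**The concern.** The aim and the assessment section describe different quantities. Aim 2 compares two sides of the brain, while the assessment section compares two tasks, both performed with the intact leg. The hypothesis is about the level of activation, but a ratio of two activations carries no information on level. The sentence that follows the ratio compares it across conditions, although conditions are what the ratio is built from. It names no arm, visit or side.

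Mechanism is one of only two specific aims, and secondary outcomes are to be tested without multiplicity correction. If numerator, hemisphere, direction and even the choice of metric stay open until the scans are read, an fMRI result in either direction could be presented as support for the hypothesis. The planned correlation with pain reduction inherits the same ambiguity of sign.

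**Working it through.** **1. The plan's own fMRI figure.** The 7 to 8 subjects cannot be reproduced, because no SD, no test and no unit (per arm or in total) are given. It can only be solved backwards as SD = change / d, where d is the detectable standardised effect. I assume that the two-sided 0.05 and 80% power stated for the primary outcome carry over.

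| Test | n | d | SD at 3% | SD at 5% |
|---|---|---|---|---|
| Paired t | 7 | 1.273 | 3/1.273 = 2.36 | 5/1.273 = 3.93 |
| Paired t | 8 | 1.156 | 3/1.156 = 2.60 | 5/1.156 = 4.33 |
| Two-sample t, n per arm | 7 | 1.632 | 3/1.632 = 1.84 | 5/1.632 = 3.06 |
| Two-sample t, n per arm | 8 | 1.507 | 3/1.507 = 1.99 | 5/1.507 = 3.32 |

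These SDs are in percentage points of BOLD signal and say nothing about the precision of a ratio. The sample size statement therefore concerns a different quantity from the coefficient in the assessment section. The point below does not depend on it.

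**2. What the ratio can register.** Write MOV and MIR for the two activations, each against rest. If treatment multiplies both by the same factor k, then (k × MOV)/(k × MIR) = MOV/MIR, and the inverse behaves likewise. So the ratio does not respond to k, whichever term is the numerator.

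**3. Illustration.** Assumed baseline: MOV = MIR = 2.0. These values are not from the documents.

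| Change after treatment | MOV | MIR | MOV/MIR | MIR/MOV | MIR − MOV |
|---|---|---|---|---|---|
| None | 2.00 | 2.00 | 1.00 | 1.00 | 0.00 |
| Both +50% | 3.00 | 3.00 | 1.00 | 1.00 | 0.00 |
| Both −50% | 1.00 | 1.00 | 1.00 | 1.00 | 0.00 |
| MIR +50% | 2.00 | 3.00 | 0.67 | 1.50 | 1.00 |
| MOV −33% | 1.33 | 2.00 | 0.67 | 1.50 | 0.67 |
| MOV +50% | 3.00 | 2.00 | 1.50 | 0.67 | −1.00 |
| MIR −33% | 2.00 | 1.33 | 1.50 | 0.67 | −0.67 |

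A rise in both, a fall in both and no change share one ratio. A rise in one condition shares its ratio with a fall in the other. The last column shows that a simple difference also cancels an equal rise in both.

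**4. Which hemispheres enter the ratio.** Take the affected side to be the cortex contralateral to the amputated limb (A), and the other side as unaffected (U). The region of interest is placed "in the respective ROI of interest – contralateral to the respective leg", and the leg meant for MIR-LEG is not defined.

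- *The leg is the moving leg.* Both tasks move the intact leg, so the ratio is MOV(U)/MIR(U). Side A is not measured.
- *For MIR-LEG, the leg is the mirrored one.* The ratio is MOV(U)/MIR(A) = [MOV(U)/MIR(U)] × [MIR(U)/MIR(A)]. The first factor is a task effect within one side, and the second is a side effect within one task. Only the product is observed, so the two cannot be separated.

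Neither reading gives a comparison of sides with the task held fixed.

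**The case against.** The best defence is that the repeated word respective suggests the second reading. MIR-LEG would then be taken over the cortex of the mirrored limb, and the ratio would be an attempt to carry out Aim 2. This is plausible, so it would be too strong to infer that the ratio has nothing to do with the side contrast. What remains is that side and task are then confounded.

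A reader might also infer that the fMRI analysis cannot show the hypothesised effect at all. The documents do not support that. The ratio moves when only one condition changes, it is described as a first step, and the planned regressors and rest condition allow activation against rest to be estimated. The path-analysis text also promises a regression of each secondary outcome on treatment. But no section commits to a level or side measure for fMRI.

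A reader might infer that the effect would appear with the wrong sign. That needs MOV-LEG as numerator, which the text does not fix. With the inverse, a rise in the mirror condition alone raises the ratio. Nor can the 3 to 5% be read as activation before and after treatment, since the plan gives it as the size of an expected change. Instability from a small denominator is a general property of ratios that nothing in the documents demonstrates here.

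Finally, relating a mirror condition to a movement control is a recognisable way to isolate a mirror-specific response. That supports keeping the ratio in a supporting role, but it does not make it a test of greater activation.

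**Conclusion.** The point holds in a limited form. The ratio, taken alone, cannot distinguish a proportional rise in both conditions from no change or from a proportional fall. Nor can it tell a rise in one condition from a fall in the other. This is true for either numerator. As specified, it is not a clean version of the Aim 2 contrast under either reading of the hemisphere wording.

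The algebra needs no assumed values; the 2.0 baseline only illustrates it. The verdict assumes that activation means an estimate against rest and that the affected side is contralateral to the amputated limb. The figure missing from the fMRI entry is captioned as a scheme of the tasks, so I do not expect it to define the analysis.

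The consequence is confined to the mechanistic aim. fMRI is a secondary outcome, is not required for eligibility, and is skipped in subjects who cannot be scanned. The primary VAS analysis is untouched. The change should still be made before any fMRI data are compared between arms.

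**What to change.** Name one fMRI outcome and use it throughout:

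- **Measure.** Pre-to-post change in percent signal change for MIR-LEG against rest, and likewise for MOV-LEG against rest, in the sensorimotor region of each hemisphere.
- **Side contrast.** Affected minus unaffected hemisphere within the same task.
- **Direction and test.** State the expected direction, and test it with a group-by-time comparison across the four arms (baseline and post-treatment scans).
- **Correlation.** Use this same measure for the correlation with pain reduction.
- **Ratio.** Keep it as a sensitivity analysis, with numerator and hemisphere stated. Do not substitute MIR-LEG minus MOV-LEG as the lead measure, since an equal rise in both conditions cancels there too.
- **Alignment.** Bring Aim 2, the fMRI assessment entry, the fMRI sentence in the sample size section and the aim 2 analysis text into line. The sample size sentence should state the SD, the test, and whether the number is per arm or in total.

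The cost is wording only. The rest condition, the regressor for each condition, the maps for both hemispheres and the two scan sessions are already planned. The downside is that the ratio becomes secondary.
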